Duration of follow up:	Patients will be followed up for a minimum of 2 years post registration into the study
Definition of end of trial:	The end of trial will be declared when the final data item from the final patient is received (i.e. it is anticipated that this will be when the final patient completes their 2-year follow-up visit).

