1.2. Trial Schema

2. INTRODUCTION

2.1. Background

2.1.1. Waldenström's macroglobulinemia

Waldenström's macroglobulinemia (WM) is a rare low grade B-cell malignancy, characterised by bone marrow infiltration with monoclonal immunoglobulin M secreting lymphoplasmacytic cells. The incidence is 5-8 cases per million, with about 1,000-1,500 new patients diagnosed in the USA annually. Incidence increases with age with a median age at diagnosis of 70 years for Caucasians, and slightly lower in other ethnic groups. There is a male to female preponderance, and an incidence higher in Caucasians than Africans or Asians (Gertz et al 2000; Gertz et al 2015).

Activating mutations in the MYD88 gene (MYD88MUT), which trigger downstream IRAK-mediated NF-κB signaling (Treon et al 2012), are seen in approximately 90% of cases. A second set of mutations with prognostic significance is found at CXCR4, the receptor for SDF-1a, which are either frameshift or nonsense mutations, are similar to those seen in the immunodeficiency syndrome WHIM (warts, hypogammaglobulinemia, infections and myelokathexis), and also lead to constitutive activation. Either or both of these mutations can be found in patients and lead to different clinical pictures, outcomes, and response to therapy (Treon, et al 2014).

According to the International Prognostic scoring system for WM (ISSWM), patients are stratified into low, intermediate, and high risk groups with respective 5-year survival rates of 87%, 68%, and 36%, based upon age, IgM level, β 2-microglobulin level, hemoglobin, and platelet count (Morel et al 2009).

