3.2. Trial Endpoints

3.2.1. Primary end-points:

- Percentage of patients achieving an overall response rate (defined as complete response (CR), very good partial response (VGPR), partial response (PR) or minor response (MR) i.e. a greater than 25% reduction in the serum IgM level) at 24 weeks post commencing treatment

3.2.2. Secondary end-points:

- Safety and tolerability of pembrolizumab and rituximab as assessed by the frequency of serious and non-serious adverse events, graded according to CTCAE v5.0
- Complete response (CR) rate at 24 weeks post commencing treatment (see appendix 4)
- Very good partial response (VGPR) rate at 24 weeks post commencing treatment (see appendix 4)
- Time to maximal response, as determined by the time of registration to the maximal disease response
- Time to next treatment, as determined by the time from registration to the next line of therapy
- Progression free survival (PFS) at 1 and 2 years
- Overall survival (OS) at 1 and 2 years
- Change in quality of life (QoL) at 24 weeks post commencing treatment

3.2.3. Exploratory endpoints:

- Assessment of PD-1 and PD-L1/ PD-L2 expression by fluorescence in situ hybridisation (FISH) and immunohistochemistry (IHC).
- IHC to assess baseline and on-treatment changes to distribution and composition of immune response cells in the microenvironment
- Analysis of baseline biopsies to elucidate potential mechanisms of action of tumour response
- Assessment of treatment outcome according to tumour genotype, as determined by sequencing assays for MYD88^{L265P} and CXCR4 mutations
- Correlation of bone marrow response with reduction in serum IgM level.
- Quantification of bone marrow involvement by morphologic assessment of trephine and flow cytometric assessment of aspirate for MRD

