17.2.2. Analysis of secondary endpoints and secondary analyses

Safety and tolerability of pembrolizumab in combination with rituximab

As this is continuous treatment, care will be taken to assess the burden of adverse events over time rather than just the worst grades seen.

Rates of adverse events (as assessed by CTCAE version 5.0) will be presented in four ways:

1. Worst grade seen of each event, i.e. the number of patients who experience a grade 1-2 or 3+ event at any time point.
2. Worst grade seen of each event per cycle, i.e. the number of patients who experience a grade 1-2 or 3+ event during each cycle.
3. Proportion of cycles where patients experience a grade 1-2 or grade 3-4 AE. This may also be presented by the number of cycles depending on the numbers of patients stopping treatment.
4. Median number of grade 1-2 or 3+ AEs (of any type) experienced at each cycle.

Analyses 3-4 may focus on clinical events only i.e. excluding lower level biochemical and haematological events which may not have an impact on the patient's quality of life.

Depending on the frequency of adverse events, we may also look at duration of some events, possibly as a proportion of the time on treatment.

AEs of special interest will be reported in more detail, with events of any grade presented.

All adverse event analysis will be descriptive.

Best response and time to best response.

The best response is the best response seen from the start of treatment; all response time points will be included.

Time to maximal response to treatment will be calculated as the time from the date of registration until the date of the best response. This will be presented as the median and range and will be reported for responding patients only.

Time to next treatment

Time to next treatment will be analysed using Kaplan-Meier survival analyses, with the time calculated from the date of registration to the date of the start of the next line of therapy. Patients who do not start a further line of treatment will be censored at the date last seen/date of death. The median (if applicable) and rates at 1 and 2 years will be presented.

Progression free survival

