Progression free survival will be analysed using Kaplan-Meier survival analyses, with the time calculated from the date of registration to the date of progression/death. Patients who are alive and progression free will be censored at the date last seen. The median (if applicable), rates at 1 and 2 years and a Kaplan-Meier curve will be presented.

Overall survival

Overall survival will be analysed using Kaplan-Meier survival analyses, with the time calculated from the date of registration to the date of death. Patients who are alive will be censored at the date last seen. The median (if applicable), rates at 1 and 2 years and a Kaplan-Meier curve will be presented.

Quality of life

Quality of life is assessed using the QLQ-30 questionnaire at baseline and at week 24. Differences between baseline and week 24 will be compared using paired t-tests and changes between baseline and week 24 may also be compared to historical data from the R2W trial.

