17.3. Interim analyses

There will be no formal interim analyses however toxicities will be monitored closely throughout the trial (see section 12.6). In addition to periodic reviews, an IDMC meeting will be triggered as a result of trial-treatment related deaths as outlined below.

An IDMC review will be triggered if the number of treatment related deaths exceeds 10% of the number of patients recruited.

Number of Patients (N)	Number of treatment related deaths needed for IDMC trigger (more than 10% of N)
10	2
15	2
20	3
25	3
30	4
35	4

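### Time to next treatment is censored at death, so if patients die without further therapy the Kaplan-Meier rates at 1 and 2 years will not equal the proportions a reader will take them for

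*Combined protocol and SAP*

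**What the plan says.** Section 3.2 lists the endpoint among the secondary endpoints: "Time to next treatment, as determined by the time from registration to the next line of therapy". Death is not part of the event.

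Section 17.2.2 gives the method, "Time to next treatment will be analysed using Kaplan-Meier survival analyses", and the censoring rule, "Patients who do not start a further line of treatment will be censored at the date last seen/date of death". The output is also specified: "The median (if applicable) and rates at 1 and 2 years will be presented". The section does not say whether a rate is the proportion who have started further therapy or the proportion who have not.

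Progression free survival, in the same section, treats death differently. It is an event there, "with the time calculated from the date of registration to the date of progression/death". No competing-risk analysis of time to next treatment is planned, and no sensitivity analysis counts death as an event.

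**The concern.** Kaplan-Meier treats a censored patient as having the same future chance of the event as those still at risk. That can be reasonable for a patient last seen alive. It cannot hold for a patient who has died, yet the rule puts both under one heading. With deaths censored, the curve describes a hypothetical population in which nobody dies before next therapy.

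Deaths within the reporting window are foreseeable:

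- Section 1.1 sets the follow-up: "Patients will be followed up for a minimum of 2 years post registration into the study".
- Overall survival at 1 and 2 years is itself an endpoint.
- Section 2.1.1 describes an older population: "Incidence increases with age with a median age at diagnosis of 70 years for Caucasians".
- Section 17.3 provides for deaths on treatment: "An IDMC review will be triggered if the number of treatment related deaths exceeds 10% of the number of patients recruited".

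At stake is the reading of one named secondary output. Someone planning a later study would take the 1- and 2-year rates as the share of patients who needed another line, or who were alive without one. The planned estimate is neither once untreated deaths occur.

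**Working it through.** **The plan's own figures.** None is stated for time to next treatment. The only design figure, 23 or more responses in 42 patients with 40% against 60%, reproduces: exact one-sided alpha 0.0375 and power 0.8032. It does not involve this endpoint.

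**Direction, by counting.** Take 42 patients with no other censoring. Suppose 4 die first without further therapy and 14 later start it.

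- Proportion who start next treatment: 14/42 = 33.3%.
- One minus Kaplan-Meier, deaths censored: 14/38 = 36.8%, which is 3.5 points higher.
- Kaplan-Meier event-free rate: 24/38 = 63.2%. Proportion alive and free of further therapy: 24/42 = 57.1%.
- With 1, 2 or 6 such deaths, one minus Kaplan-Meier is 14/41 = 34.1%, 14/40 = 35.0% or 14/36 = 38.9%, against the same 33.3%.

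One minus Kaplan-Meier is never below the cumulative incidence. It is strictly above it once an untreated death precedes a later treatment start.

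**Size, with assumed constant yearly hazards.** Let a be the hazard of next treatment and b the hazard of death without it. Both are assumptions; the documents give neither.

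- One minus Kaplan-Meier: 1 − exp(−a·t)
- Cumulative incidence: a/(a+b) × [1 − exp(−(a+b)·t)]
- Alive and free of further therapy: exp(−(a+b)·t)

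Base case, a = 0.35 and b = 0.08:

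- 1 year: 1 − exp(−0.35) = 29.5%; (0.35/0.43) × [1 − exp(−0.43)] = 28.4%. Gap about 1.1 points.
- 2 years: 1 − exp(−0.70) = 50.34%; (0.35/0.43) × [1 − exp(−0.86)] = 46.95%. Gap 3.4 points before rounding, or 3.3 from the rounded 50.3% and 47.0%.
- 2 years, event-free reading: exp(−0.70) = 49.7% by Kaplan-Meier, against exp(−0.86) = 42.3% alive and free of further therapy.

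Across a = 0.20 to 0.50 and b = 0.03 to 0.20, the 2-year overstatement runs from 0.9 points (33.0% against 32.1%) to 9.4 points (63.2% against 53.8%).

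**A second range.** This one fixes the 2-year value of one minus Kaplan-Meier and the net 2-year risk of death without next treatment. Entries are the overstatement in percentage points at 2 years.

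| Net risk of death | 1−KM = 20% | 1−KM = 40% | 1−KM = 60% |
|---|---|---|---|
| 2% | 0.2 | 0.4 | 0.5 |
| 5% | 0.5 | 0.9 | 1.3 |
| 10% | 1.0 | 1.9 | 2.6 |
| 15% | 1.5 | 2.8 | 3.9 |
| 20% | 2.0 | 3.8 | 5.3 |

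For the 40% column, the 1-year overstatement is 0.1 to 1.2 points.

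**How extreme is a death hazard of 0.20?** Section 2.1.1 quotes 5-year survival of 87%, 68% and 36% for low-, intermediate- and high-risk disease. At a constant hazard these give −ln(0.87)/5 = 0.028, −ln(0.68)/5 = 0.077 and −ln(0.36)/5 = 0.204 a year. They are all-cause figures from a prognostic score, so they are only a guide. Only deaths before next therapy compete.

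**The case against.** The case for leaving the text alone has several parts, and most of it stands as a limit on size.

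- **Convention.** Censoring at death is common and the rule is explicit. A Kaplan-Meier curve of this kind can be interpreted if it is labelled for what it is. That is a reason to keep the curve as a supplement; it does not make the 1- and 2-year values proportions of patients.
- **Undefined rate.** A reader might infer that the plan commits to reporting one minus Kaplan-Meier as the share going on to further therapy. The text does not say so; the treatment-free rate may be meant. The point is therefore conditional on the reading, but neither reading escapes it: the complement carries the same error, and as a share alive and untreated the Kaplan-Meier value is also too high.
- **Size.** A reader might take 9.4 points as a likely error. The documents do not support that. It needs every patient to have about the all-cause mortality of the high-risk group, every death to fall before next therapy, and the highest treatment hazard in the range. Even 0.08 is close to the whole all-cause hazard of the intermediate group.
- **Precision.** Near 50% with 42 patients, the binomial standard error is √(0.5 × 0.5/42) = 7.7 points. The base-case gap is under half of that, about 1.4 patients. This is true, but sampling error shows in a confidence interval and this bias does not.
- **Consequence.** A reader might infer that deaths are hidden or that the trial's conclusion is at risk. Neither follows. Progression free survival counts deaths, overall survival is reported at the same times, and no threshold or comparison is attached to time to next treatment.

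**Conclusion.** The concern holds in a limited form. The plan censors at an event after which next treatment is impossible. Once a death without further therapy precedes a later treatment start, one minus the Kaplan-Meier rate is too high as an estimate of the proportion starting next treatment. The event-free rate is too high as the proportion alive without it.

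The direction is mathematical. The size rests on assumed hazards: about 1.1 points at 1 year and 3.3 to 3.4 points at 2 years in the base case, and about 1 point or less with few deaths. The 9.4-point figure is an outer bound under extreme assumptions and should not be quoted as the expected error. This is a descriptive secondary endpoint; the response analysis, the sample size of 42 and the 23-response rule do not depend on it. The change is still worth making, because the output is named in the plan and the correction is simple.

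**What to change.** In section 17.2.2, under time to next treatment:

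1. Report the 1- and 2-year rates as the Aalen-Johansen cumulative incidence of starting next treatment, with death before next treatment as a competing event and with confidence intervals. Censor at the date last seen only those alive without further therapy.
2. State that this cumulative incidence is what the rate means.
3. Keep the Kaplan-Meier curve, if wanted, as a supplement labelled as censoring deaths.
4. If a median is wanted, either take it from the cumulative incidence curve (where it reaches 50%) or report time to next treatment or death. The latter should be labelled as a separate composite, because it differs from the endpoint in section 3.2 and partly overlaps progression free survival.

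The cost is a small wording change and slightly more analysis work. The text sits in the protocol, so the change goes through the amendment process in section 18.4. No new data are needed: dates of next therapy and of death are already required for the planned analyses.

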9.4. Assessments after treatment discontinuation (for reasons other than disease progression)

If patients complete treatment or are withdrawn from trial treatment early, for reasons other than disease progression the following assessments are to be performed on day 60 (+/- 3 days) following treatment discontinuation:

- Clinical examination: physical examination (including assessment of lymph node, liver and spleen size)
- Concurrent medication assessment
- Adverse event assessment
- Blood pressure
- Weight
- Assessment of ECOG performance status (see appendix 3)
- Full blood count (including red blood cell (RBC), haemoglobin (Hb), white blood cell (WBC) absolute neutrophil count (ANC), absolute lymphocyte count (ALC), haematocrit and platelets)
- Biochemistry (including bicarbonate, uric acid, albumin, alkaline phosphatase (ALP), alanine/aspartate transaminase (ALT/AST), total bilirubin, calcium, creatinine, potassium, sodium, glucose, urea, and estimated glomerular filtration rate (eGFR), U&E, liver function tests (LFT), LDH, and amylase)
- TSH, glucose and ACTH tests

Patients will then be assessed at 5 months (+4 weeks) after the date of treatment discontinuation, over the phone or at a standard hospital visit for the purposes of:

- Adverse event assessment

Patients are then followed up for the trial annually from the date of treatment discontinuation for the following:

- Remission status assessment (investigations as per local protocols)

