11. DATA MANAGEMENT AND DATA HANDLING GUIDELINES

Data will be collected from sites on version controlled case report forms (CRFs) designed for the trial and supplied by UCL CTC. Data must be accurately transcribed onto trial CRFs and must be verifiable from source data at site. Examples of source documents are hospital records which include patient's medical notes, laboratory and other clinical reports etc.

Where copies of supporting source documentation (e.g. autopsy reports, pathology reports, CT scan images etc.) are being submitted to UCL CTC, the patient's trial number must be clearly indicated on all material and any patient identifiers removed/blacked out prior to sending to maintain confidentiality.

Please note that, for this trial, patients must consent to their NHS/CHI number being supplied to UCL CTC. This is required in order to allow for follow up via national registries where needed.

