15.4. Losses to Follow-Up

If a patient moves from the area, every effort should be made for the patient to be followed up at another participating trial site and for this new site to take over the responsibility for the patient, or for follow-up via GP. Details of participating trial sites can be obtained from the UCL CTC trial team, who must be informed of the transfer of care and follow up arrangements. If it is not possible to transfer to a participating site, the registering site remains responsible for submission of forms.

If a patient is lost to follow-up at a site every effort should be made to contact the patient's GP to obtain information on the patient's status.

At the time of loss to follow up, the following CRFs should be submitted:

- Change of status form
- All CRFs due up to and including the date of loss to follow up

If contact is re-established with the patient, further follow up forms should be sent, including notifications of progression. A death form should also be submitted if the site becomes aware the patient has died.

Prior to primary analysis and presentation/publication of the primary endpoint data, UCL CTC will ask sites to attempt to re-establish contact with patients who were lost to follow up and/or check hospital records for evidence of when the patient was last known to be alive and evidence of disease progression and death.

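### PFS is censored at the date last seen, which is not tied to a disease assessment, so some patients can be credited with progression-free time in which IgM progression could not be observed

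*Combined protocol and SAP*

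**What the plan says.** **Analysis (section 17.2.2).** PFS runs "with the time calculated from the date of registration to the date of progression/death". The censoring rule is "Patients who are alive and progression free will be censored at the date last seen". For OS it is "Patients who are alive will be censored at the date last seen". For both endpoints, "The median (if applicable), rates at 1 and 2 years and a Kaplan-Meier curve will be presented". Section 17 does not define the date last seen, has no rule based on the last adequate assessment, and plans no sensitivity analysis for PFS.

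**Follow-up after stopping without progression (section 9.4 and Appendix 1).**
- Day 60: physical examination (including nodes, liver and spleen), blood count, biochemistry and endocrine tests. IgM and paraprotein are not listed.
- 5 months: a contact "over the phone or at a standard hospital visit for the purposes of" adverse event assessment, and nothing else.
- Annually from the date treatment stopped: "Remission status assessment (investigations as per local protocols").

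**Tracing (section 15.4).** For patients lost to follow-up, sites are asked to "check hospital records for evidence of when the patient was last known to be alive and evidence of disease progression and death".

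**Progression (Appendix 3).** An IgM rise of at least 25% from nadir, which should be confirmed by a second measurement, and/or progression in clinical features attributable to the disease.

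**The concern.** A date on which a patient is known to be alive is a sound censoring date for OS. For PFS the date also has to be one on which the patient was known not to have progressed. An IgM rise is a laboratory finding, and a telephone call about adverse events cannot reveal it.

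A patient last assessed for disease at one date and last contacted some months later counts as at risk over the interval, although an IgM progression in it would go unrecorded. The denominator is too large for the events that can be observed, so the estimated hazard is too low and PFS too high. OS is not affected.

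PFS at 1 and 2 years is a named secondary endpoint. The trial has a single arm, so no control group shares the bias, and section 2.1.2 describes earlier relapse therapy by its median PFS, the natural yardstick for a reader.

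**Working it through.** **1. The plan's own figure.** The only design calculation is for response (section 17.1): null rate 40%, target 60%, one-sided alpha 0.05, power 80%, 42 patients, success at 23 or more responses. Exact binomial: P(X ≥ 23 | n = 42, p = 0.40) = 0.0375 and P(X ≥ 23 | n = 42, p = 0.60) = 0.803. No smaller n meets both limits, so the design reproduces. PFS does not enter it.

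**2. Who is affected.** Only patients without recorded progression whose last contact is not a disease assessment. Anyone who reaches a later annual remission assessment has the earlier call superseded.

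**3. Formula.** Let g be the share of patients event-free at the start of the gap who have no disease assessment during it but are counted as at risk to its end. Let R be the proportion of the remaining patients who get through the gap without a *recorded* event. Nobody is censored inside the gap, so across it Kaplan-Meier gives g + (1 − g)R under the date-last-seen rule and R under a last-assessment rule. At a later time t the overstatement is

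S(t) × g × (1/R − 1).

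**4. Inputs.** Exponential PFS with median 16 or 24 months (the range in section 2.1.2, used as an illustration). S(24) = 0.354 or 0.500. The documents give no loss rate, so g = 5 to 20% is an assumption.

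**5. Completers lost after the call at about month 17.** The gap is months 12 to 17. True survival over 5 months is 2^(−5/16) = 0.805 or 2^(−5/24) = 0.866.
- Progression found only at scheduled visits: none is scheduled in the gap, so R = 1 and the overstatement is 0.
- Half of progressions surface between visits: R = 1 − 0.5 × (1 − 0.805) = 0.903, or 1 − 0.5 × (1 − 0.866) = 0.933. So 1/R − 1 = 0.108 or 0.072.

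| Median | g = 5% | g = 10% | g = 20% |
|---|---|---|---|
| 16 months | 0.354 × 0.05 × 0.108 = 0.2 points | 0.4 | 0.8 |
| 24 months | 0.500 × 0.05 × 0.072 = 0.2 points | 0.4 | 0.7 |

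**6. Early stoppers.** Treatment stops without progression at about 4 months, the adverse-event-only call comes at about 9 months, and the patient is then lost. The other patients have IgM before each 3-weekly cycle (section 9.2.1), so progression is seen throughout. From the cycle visit at 4.14 months to the last one before month 9 is 7 × 21 days = 4.83 months. R = 2^(−4.83/16) = 0.811 or 2^(−4.83/24) = 0.870, so 1/R − 1 = 0.233 or 0.150. S at the end of 18 cycles (12.4 months) is 0.584 or 0.699.

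| Median | Time | g = 5% | g = 10% | g = 20% |
|---|---|---|---|---|
| 16 months | 1 year | 0.584 × 0.05 × 0.233 = 0.7 points | 1.4 | 2.7 |
| 24 months | 1 year | 0.699 × 0.05 × 0.150 = 0.5 points | 1.0 | 2.1 |
| 16 months | 2 years | 0.4 | 0.8 | 1.6 |
| 24 months | 2 years | 0.4 | 0.7 | 1.5 |

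Kaplan-Meier simulations with 42 patients agree with both sets of results to within about 0.1 point.

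**7. Scale.** With 42 patients and no censoring, the standard error of 2-year PFS is √(0.354 × 0.646/42) = 7.4 points or √(0.5 × 0.5/42) = 7.7 points.

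**The case against.** **The call rarely sets the censoring date.** Remission status is assessed annually, and section 8.11 follows disease status yearly until the last patient completes 2 years. This stands: the bias needs a patient lost after the call and before the next annual assessment.

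**Progression can still come to light.** The 5-month contact may be a hospital visit, progression includes clinical features, the day-60 visit examines nodes and spleen, and section 12.5 requires confirmed progression to be reported within 72 hours. Tracing under section 15.4 asks for evidence of progression as well as the last date alive. This stands in part. These routes capture progressions that someone has found, but they do not set a suitable censoring date for a patient whose IgM was not measured.

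**Stronger readings.** Two are tempting.
- A reader might infer that a registry contact counts as the date last seen, because section 11 says of the NHS/CHI number: "This is required in order to allow for follow up via national registries where needed". That sentence permits registry follow-up, but nothing says that a registry date is a date on which the patient was seen. The point does not need this route.
- A reader might size the completer route as if all other patients' progressions were detected continuously in months 12 to 17, which roughly doubles the half-detection figures. The protocol schedules no IgM test in that interval, so its schedule does not support this.

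**Little depends on it.** PFS is descriptive, with no test or threshold, and the decision rule is 23 or more responses. This stands and limits the weight of the point.

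**Conclusion.** The point holds as a flaw in the wording of the censoring rule, with a modest effect confined to patients whose last contact is not a disease assessment. The direction is upward for 1-year and 2-year PFS; the size cannot be fixed from the documents. If every patient's last contact is a disease assessment, the bias is zero.

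Under the assumptions shown, the completer route gives 0 to about 0.8 points at 2 years. The early-stop route gives up to about 0.5 to 2.7 points at 1 year. The early-stop figures also assume that the 24-week and 1-year response assessments are not done once treatment has stopped. They sit under assessments during treatment (section 9.2), and section 9.4 does not repeat them; if they are done, the gap and the bias shrink. The effect of last-known-alive dates from tracing has not been sized.

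All these figures are well below the standard error of 7 to 8 points for 2-year PFS. The primary endpoint, the 42-patient design and OS are unaffected. The case for change is that the better rule is cheap.

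**What to change.** In the PFS paragraph of section 17.2.2, replace the censoring date with: *the date of their last disease assessment (serum IgM/paraprotein result or remission-status assessment) showing no progression*. Keep the date last seen for OS. Report PFS under the date-last-seen rule as a sensitivity analysis.

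**Cost.** One sentence and one extra Kaplan-Meier estimate, with no new visits or tests. IgM and remission assessments are already scheduled, but the case report forms are not in the documents, so the team should confirm that assessment dates are captured.

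**Downsides.** PFS follow-up becomes slightly shorter for some patients. Deaths after the last assessment still count as events while living patients are censored back to that assessment, which thins the risk set selectively and can bias PFS slightly downward. Showing both versions brackets the two effects. Remission status follows local protocols and need not include IgM, so the new rule narrows the gap without closing it entirely.
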